Baseline data: Once screened, consented, and enrolled, the following demographic data will be collected: birthdate, gender, race, time of arrival to the ED, details of any treatment by a referring provider, symptom type and duration (hours), time since last inhaled bronchodilator (minutes), time since systemic corticosteroids (minutes), number and type of inhaled bronchodilator treatments in the preceding 24 hours, all home medications, drug and food allergies, past medical history, number of hospital admissions for asthma over the prior 12 months, and number of ICU admissions over the child's lifetime. Initial temperature, respiratory rate, heart rate, blood pressure, and pulse oximetry will be recorded. Finally, height, PEFR, and CAS will be measured by the respiratory therapist (RT) immediately prior to the study intervention. Additionally, the subject's family will be asked to complete an Asthma Control Tool (ACT). The ACT is a measure of how well the participant's asthma has been controlled over the preceding three months.

Intervention: Subjects will then be randomly assigned (50% chance) to receive a weight based dose of IM epinephrine 1:1000 or no adjunctive medication. The dose will be 0.2 mg for subjects 20-30 kg and 0.3 mg for subjects greater than 30 kg. This will be injected intramuscularly by an ED nurse into the anterior thigh muscles of the subject using a 1 ml syringe and a 23 gauge one inch needle.

In addition to the study intervention, the standardized treatment pathway based on the current asthma guidelines in use at our center will be utilized. This pathway includes nebulized albuterol, ipratropium bromide, and systemic corticosteroids. The duration and dosages of these other interventions will be administered at the discretion of the treating provider.

Randomization: A block randomization scheme will be used to promote balance at the end of the study. Block randomization ensures that after each block of individuals are enrolled in the study (n individuals in total); an equal number of individuals will be assigned to each group (n/2 individuals in each group). We will use random block sizes of 8-12.

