Allocation concealment: The RT will be blinded as to whether the subject receives a dose of IM epinephrine. Once a patient is determined to be eligible for the study, the research team will complete informed consent/assent. A pharmacy generated randomization schedule will be utilized and sealed envelopes with the allocations (treatment or control) will be kept in the charge nurse's office.

At the time of allocation, the charge nurse will instruct all staff to leave the subject's room. The charge nurse will then open the designated envelope and personally prepare and administer IM epinephrine if the subject is allocated to the treatment arm. If the subject is allocated to the control arm, the charge nurse will draw up a syringe with the appropriate amount of saline as if an injection of epinephrine was going to be given to the participant. The charge nurse will take this syringe into the subject's room, but not administer it. Instead, a 'sham' Band-Aid will be placed over the thigh of the subject. They will be instructed not to reveal to the RT, research team, or bedside nurse whether or not an injection was actually given. Participants and families will be similarly instructed. The RT will remain blinded throughout and will be responsible for measuring all PEFRs and CASs.

Having block sizes that are randomly determined, as well as having larger block sizes of 8-12 will help minimize a member of the research team or the RT guessing the allocation of the next participant and potentially biasing recruitment or assessment. To further assess blinding, at the conclusion of the study, we will ask the RTs to guess which group the subjects they assessed were in.

Study data: The following data will be measured at time points (t_{15} , t_{30} , t_{60} , t_{90} , and t_{120}) minutes following IM epinephrine or sham drug administration: PEFR (if able), CAS, heart rate, respiratory rate, and pulse oximetry. This data will also be recorded at the time of discharge or admission from the ED. Also recorded will be amount and timing of bronchodilator, anticholinergic, and corticosteroid therapy given. Additionally, any other therapies and interventions will be recorded (i.e. oxygen administration, assisted ventilation, magnesium sulfate administration, etc.). ED length of stay as well as disposition will be noted.

Primary outcome measure: Change in percent of predicted PEFR/CAS 15 minutes after the study intervention (t_{15}).

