Secondary outcome measures:

1. Change in percent of predicted PEFR/CAS at t₁₅

- 2. Disposition
- 3. Change in percent of predicted PEFR/CAS at t₃₀, t₆₀, t₉₀ and t₁₂₀
- 4. Change in percent of predicted PEFR/CAS at t₃₀, t₆₀, t₉₀ and t₁₂₀
- 5. Change in respiratory rate at t_{15} , t_{30} , t_{60} , t_{90} and t_{120}
- 6. Change in heart rate at t_{15} , t_{30} , t_{60} , t_{90} and t_{120}
- 7. Need for supplemental oxygen at t_{60} , t_{90} and t_{120} (defined as a room air pulse oximetry of <93%)
- 8. Need for albuterol at t_{60} , t_{90} and t_{120}
- 9. Number of hours of albuterol therapy
- 10. ED length of stay

Statistical analysis plan: First straightforward tests for differences among the two groups of individuals will be performed. Analysis of Variance (ANOVA) techniques will be used to test for differences among continuous variables, while Kruskal-Wallis, Fischer's Exact Tests and Wilcoxon methods will be used to test for differences among categorical variables. To examine the outcomes of: (1) change in percent of predicted PEFR/CAS, (2) respiratory rate, (3) heart rate, (4) hours of albuterol therapy and (5) length of stay in the ED, separate mixed-effects general linear models will be developed for each outcome (five models will be developed). The two arms (IM epinephrine and no epinephrine) will be analyzed as fixed effects, and time (time since randomization) will be analyzed as a repeated measures effect. Traditional risk factors (e.g. age, gender, and ethnicity) will be incorporated as covariates during secondary analyses. All main effects and all two-way interaction effects will be investigated for significance from the mixed-effects models developed. Negative binomial regression and logistic regression techniques will also be used to evaluate (7) need for supplemental oxygen and (8) need for albuterol. Life table analysis and Kaplan-Meier techniques will initially be used to analyze the time-related variables (e.g., time to discharge). The Log-rank test will be used to test for differences among survival curves. In addition, Cox (proportional hazards) regression techniques will be developed to test for differences among groups as well as allow for adjustment for additional covariates and risk factors. Cox regression will allow us to investigate all potential main effects and interaction effects. All statistical analyses will be performed by a statistician who is blinded to the treatment allocation of the two groups.

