Planned interim analysis: Interim analyses, reported to the data monitor will be performed at 6, 9 and 12 months after the first participant is randomized. A Lan-DeMets spending function approach will be used to monitor the need for early trial termination.

Power calculation: We will develop separate mixed-effects general linear models for each of the outcomes. For a sample size (n=54) the study has 81% power to detect a 12% main effect of each treatment for each outcome. The estimated power for detecting a 5% interaction effect is 32%. The total sample size required to achieve 80% power to detect an interaction effect, based on the full-factorial designed proposed, is n=1728; which is not a feasible number in which to recruit and enroll. In addition, we will develop Cox proportional hazards regression models to assess the association between group assignment and time related outcomes. For the anticipated sample size (n=54), this study has 80% power to detect a hazards ratio of 1.82 with two-sided α =0.05. Lastly, multiple logistic regression techniques will be utilized to assess

the association between group assignment and dichotomized outcomes. Using the dichotomized version of some outcomes, this study has 80% power to detect on odds ratio of 1.58 with a two sided α =0.05 (n=54). Therefore, we have more than sufficient numbers of participants in each comparison group.

We anticipate that less than 10% of all potential participants will drop out. Therefore, we will recruit a total of 60 individuals for the current study (n=30 per group). This is a feasible sample size for the research team to recruit and enroll in the current study. Power calculations were based on the anticipated total sample size (n=54) that will be available for complete analysis. Using a block randomization scheme (with random block sizes of 8-12), we anticipate that n=30 participants will be assigned to each group.

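### The main mixed model for change in PEFR/CAS does not adjust for the outcome's own baseline, which is measured just before treatment, so the t15 estimate is usually less precise than it could be

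*Combined protocol and SAP*

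**What the plan says.** The primary outcome measure is "Change in percent of predicted PEFR/CAS 15 minutes after the study intervention". For the main analysis, the statistical analysis plan states that "The two arms (IM epinephrine and no epinephrine) will be analyzed as fixed effects", with time since randomization as a repeated-measures effect; two-way interactions are also examined. Other covariates come later: "Traditional risk factors (e.g. age, gender, and ethnicity) will be incorporated as covariates during secondary analyses". That list is open-ended, but it is confined to secondary analyses and does not name baseline PEFR or CAS.

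The data exist. Under Baseline data, "height, PEFR, and CAS will be measured by the respiratory therapist (RT) immediately prior to the study intervention". For the vital signs, "Initial temperature, respiratory rate, heart rate, blood pressure, and pulse oximetry will be recorded".

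Under Randomization, "A block randomization scheme will be used to promote balance at the end of the study"; the text explains that this means equal numbers per arm. No stratification by baseline severity is described. The Power calculation section says that, with 54 analyzed children, "the study has 81% power to detect a 12% main effect of each treatment for each outcome". It gives no SD, no baseline-to-follow-up correlation and no baseline adjustment.

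**The concern.** A change score uses baseline in one fixed way: it assumes that each extra point at baseline carries through as one extra point at t15. If the true slope differs from 1, the change score still depends on baseline, and that dependence stays in the error term. An analysis that estimates the slope removes it.

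Two things follow. The standard error of the t15 difference is usually larger than it needs to be. And in the one trial that is run, the estimate moves with whatever chance baseline difference arises between two arms of about 27, because blocking balances numbers and not severity. With 54 children, one primary time point and a claimed power of only 81%, information already collected is worth using.

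Respiratory rate and heart rate appear as changes in the secondary outcomes but without that word in the list of models. If they are modelled as raw post-treatment values, the baseline slope is fixed at 0 instead of 1, and the same omission applies.

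**Working it through.** **Inputs from the documents.** 54 analyzed children with 1:1 allocation, so 27 per arm; a 12% effect; 81% power (Power calculation). Two-sided 0.05 is stated there for the hazard-ratio and odds-ratio calculations and is assumed here for the mixed model.

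**Inputs not in the documents (assumed).** The 12% is read as 12 percentage points at t15 in a two-sample t-test. *r* is the correlation between baseline and t15, and *k* = SD(t15)/SD(baseline). The baseline slope is then *rk*.

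**Step 1: the plan's own figure.** The 81% cannot be reproduced independently, because no SD is given. Solving for the SD that yields it gives 15.25 (t-test) or 15.5 (normal approximation). I use 15.25, so the SE of the unadjusted difference is 15.25 × √(2/27) = 4.15 points.

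**Step 2: variance ratio.** In units of the baseline variance, the change score has variance 1 + k² − 2rk, and the baseline-adjusted residual has variance k²(1 − r²). Hence

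ratio = k²(1 − r²) / (1 + k² − 2rk), which is (1 + r)/2 when k = 1.

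**Step 3: power.** Adjusted power uses SD = 15.25 × √ratio. The last column also charges for estimating the slope (variance × [1 + 1/(54 − 4)] = 1.02, with 51 df).

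| k | r | slope | ratio | power | power, slope cost charged |
|---|---|---|---|---|---|
| 1 | 0.3 | 0.30 | 0.65 | 0.941 | 0.936 |
| 1 | 0.5 | 0.50 | 0.75 | 0.906 | 0.900 |
| 1 | 0.7 | 0.70 | 0.85 | 0.868 | 0.861 |
| 1.25 | 0.3 | 0.38 | 0.78 | 0.893 | 0.887 |
| 1.25 | 0.5 | 0.63 | 0.89 | 0.852 | 0.844 |
| 1.25 | 0.7 | 0.88 | 0.98 | 0.817 | 0.810 |
| 1.5 | 0.3 | 0.45 | 0.87 | 0.860 | 0.853 |
| 1.5 | 0.5 | 0.75 | 0.96 | 0.824 | 0.816 |
| 1.5 | 0.7 | 1.05 | 1.00 | 0.811 | 0.803 |
| 2 | 0.3 | 0.60 | 0.96 | 0.826 | 0.819 |
| 2 | 0.5 | 1.00 | 1.00 | 0.810 | 0.802 |
| 2 | 0.7 | 1.40 | 0.93 | 0.838 | 0.831 |

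The comparator is 0.81 throughout. At k = 1, 54 children analyzed by change score carry the information of about 54 × 0.65 = 35, 54 × 0.75 = 41 and 54 × 0.85 = 46 children analyzed with adjustment.

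**Step 4: simulation.** Eleven of these twelve pairs (all but k = 1.5, r = 0.3) were simulated, with 20,000 trials each and a true effect of 12. Mean estimates were 11.96 to 12.05 for both methods, so neither is biased. Adjusted power was 0.935, 0.902 and 0.861 at k = 1, and 0.802 to 0.886 for k from 1.25 to 2. At slope 1 (k = 2, r = 0.5) it was 0.802 adjusted against 0.812 unadjusted.

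**Step 5: shift within a given trial.** If the arms differ at baseline by D, the expected change-score estimate is the true effect plus (slope − 1) × D. Take D equal to one SE of the baseline difference, SD(baseline) × √(2/27), where SD(baseline) = 15.25/√(1 + k² − 2rk). A difference at least this large, in either direction, arises in about 32% of trials.

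- k = 1, r = 0.5: D = 4.15, shift (0.5 − 1) × 4.15 = −2.07 points.
- k = 2, r = 0.5: slope 1, shift 0.
- k = 2, r = 0.7: SD(baseline) = 10.28, D = 2.80, shift (1.4 − 1) × 2.80 = +1.12 points.

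**Step 6: raw respiratory and heart rate.** If these are modelled raw, with the pre-treatment value left out altogether, the ratio is 1 − r² = 0.91, 0.75 and 0.51 at r = 0.3, 0.5 and 0.7.

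**The case against.** The strongest reply is that baseline is already used, by subtraction, and that the remaining benefit depends on r and k, which the documents do not give. Entry requires PEFR below 60% of predicted or a CAS of at least 7, which can narrow the baseline spread relative to t15 (k above 1). The gain is then smaller. At r = 0.7 and k of 1.25, 1.5 and 2, formula power is only 81.7%, 81.1% and 83.8%. The case k = 1, r = 0.7 also needs a baseline SD of 15.25/√0.6 = 19.7 points. A uniform spread from 0 to 60% would have an SD of only 60/√12 = 17.3, although children who enter on CAS alone are not capped at 60%. All of this stands: the equal-SD figures are the favorable end of the range.

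The anchor is also an assumption. The power statement concerns a main effect for each outcome, not a t15 contrast in PEFR. Since PEFR is taken only when the child is able, fewer than 27 per arm may contribute. The absolute powers and point shifts therefore carry that uncertainty. The variance ratios do not depend on the anchor.

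For respiratory and heart rate, the plan may intend change scores, or may include the pre-treatment value as a repeated measure; the ratios in step 6 would not then apply. Those vital signs are also described only as initial values, not as taken immediately before the intervention.

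The open-ended covariate list does not answer the point, because anything read into it stays in secondary analyses. Nor does the search for two-way interactions, which adds no baseline term.

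**Conclusion.** The concern holds as an efficiency point, not a validity defect. The main model names only arm and time, and the t15 estimate is usually less precise than the collected data allow. Across the settings examined, adjustment changes power by about −1 point (slope 1 or close to it) to +13 points (equal SDs, r = 0.3). This rests on a change SD of 15.25 inferred from the stated 81% and on assumed r and k. Which setting applies cannot be known from the documents; the severity restriction at entry makes a smaller gain plausible. The direction of any shift from chance imbalance is likewise unknown, because it depends on whether the slope is below or above 1. The balance is still uneven: a loss of about 1 point at worst, against a gain of roughly 5 to 13 points if the SDs are similar and r is 0.3 to 0.7. The change should be made.

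**What to change.** In the main mixed model for each repeated outcome, add that outcome's own pre-intervention value as a fixed covariate, with a baseline-by-time term so that the slope can differ by time point. Use baseline percent-predicted PEFR in the PEFR model, baseline CAS in the CAS model, and the recorded initial respiratory rate and heart rate in theirs. State that PEFR and CAS are fitted as separate models, so that each has its matching baseline. Include the arm-by-time term and name the adjusted arm difference at t15, with its 95% CI, as the primary estimate. Keep age, gender and ethnicity for secondary analyses.

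The cost is a short SAP edit and a few degrees of freedom, or about 1 point of power in the worst case simulated. No new data are needed, and no further child is lost, because a change score already requires the same baseline value. The choice should be fixed before outcome data are seen, so that adjusted and unadjusted estimates are not selected between afterwards.

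### All two-way interactions are tested for significance in five models without multiplicity control and with conceded low power, so a chance interaction is likely

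*Combined protocol and SAP*

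**What the plan says.** The Statistical analysis plan sets up five mixed models: percent predicted PEFR/CAS, respiratory rate, heart rate, hours of albuterol, and ED length of stay. Arm is a fixed effect and "time (time since randomization) will be analyzed as a repeated measures effect". The text continues: "Traditional risk factors (e.g. age, gender, and ethnicity) will be incorporated as covariates during secondary analyses". The next sentence is the one at issue: "All main effects and all two-way interaction effects will be investigated for significance from the mixed-effects models developed". For time-to-event outcomes it adds that "Cox regression will allow us to investigate all potential main effects and interaction effects".

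The Power calculation section states: "For a sample size (n=54) the study has 81% power to detect a 12% main effect of each treatment for each outcome". It then gives 32% power for a 5% interaction and a total of 1728 for 80% power to detect an interaction, "which is not a feasible number in which to recruit and enroll".

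Neither section lists the interactions, adjusts for their number, says whether a significant one stays in the model, fixes the coding of covariates, or says which model supplies the effect of epinephrine.

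**The concern.** The plan commits to a large, open-ended set of significance tests in about 54 children, and its own power section says such tests cannot be adequately sized here. Followed literally, it is more likely than not to produce a nominally significant subgroup, time or covariate pattern when none exists. In a small trial, such a pattern can be reported as a finding about which children respond to epinephrine.

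There is a second, conditional risk. Once an arm-by-covariate term is in a model with reference coding, the arm coefficient is the effect in the reference subgroup, not the average effect. It is also estimated less precisely. The plan does not say that this coefficient will be reported as the treatment effect, but it does not name another.

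**Working it through.** **Inputs.** Five models, arm and time as factors, and age, gender and ethnicity as named covariates (Statistical analysis plan). n=54, 81% power for a 12% main effect, 32% for a 5% interaction, and 1728 for 80% interaction power (Power calculation). Two-sided α=0.05 is stated only for the Cox and logistic calculations and is assumed for interactions. One degree of freedom per term is also assumed.

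**1. The plan's own figures.** No SD is given. With 27 per arm, power = Φ(δ/SE − 1.96), where SE = SD·√(2/27). For 81%, δ/SE = 1.960 + 0.878 = 2.838, so SE = 12/2.838 = 4.23 and SD ≈ 15.5.

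With that SD, a 5-point interaction has this two-sided power:
- as a difference of differences, SE = 2 × 4.23 = 8.46: Φ(5/8.46 − 1.96) ≈ 9%, and N for 80% ≈ 1213;
- with half coding, SE = 4.23: Φ(5/4.23 − 1.96) ≈ 22%, and N for 80% ≈ 303.

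Neither matches 32% or 1728. Nor do those two figures fit one effect. Power of 32% at 54 scales to N = 54 × (2.802/1.492)² ≈ 190, while 80% at 1728 implies Φ(2.802·√(54/1728) − 1.96) ≈ 7% at 54. The text does not give the effect size behind 1728, so it may differ from 5%. On either reading, interaction power is low.

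**2. Number of tests.** Hours of albuterol and ED length of stay have one value per child, so time interactions do not exist for them.
- Three repeated outcomes, five factors: C(5,2) = 10 each, 30 in total.
- Two single-value outcomes, four factors: C(4,2) = 6 each, 12 in total.
- Total 42. Terms involving arm: 3 × 4 + 2 × 3 = 18.

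The covariate list is open, so three covariates is a minimum once covariates are included.

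**3. False positives when no interaction exists.** Independent tests: 1 − 0.95^k.

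| Tests | k | P(at least one p<0.05) |
|---|---|---|
| Arm-by-time, three repeated outcomes | 3 | 14% |
| One repeated-outcome model | 10 | 40% |
| All terms involving arm | 18 | 60% |
| All interactions | 42 | 88% |

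The expected number of false positives is 42 × 0.05 = 2.1.

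Outcomes in the same child are correlated. The joint probability was therefore simulated (3,000 null trials per setting; 27 per arm; age uniform 6–18; gender 50%; binary ethnicity 40%; five visits; time interactions tested on linear slopes):

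| Correlation of the between-child component across outcomes | Any of 42 | Any of 18 involving arm |
|---|---|---|
| 0 | 87% | 60% |
| 0.3 | 86% | 57% |
| 0.6 | 80% | 50% |
| 0.9 | 73% | 42% |

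**4. Arm effect if interactions are kept.** With k balanced binary covariates, each interacting with arm and reference-coded, the variance of the arm coefficient is multiplied by 1 + k. Power = Φ(2.838/√(1+k) − 1.96): 81% for k=0, 52% for k=1, 37% for k=2, 29% for k=3.

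Simulation (8,000 trials per setting, standardised effect 0.77, one value per child, the three covariates in every model, age centred):

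| Interactions kept | Reference-coded binaries | Centred coding |
|---|---|---|
| None | 78% | 77% |
| Arm × gender | 47% | 77% |
| Arm × gender, arm × ethnicity | 38% | 77% |
| All three arm × covariate | 38% | 77% |
| All six | 35% | 74% |

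The loss comes from how the coefficient is coded and read, not from having tested an interaction.

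**The case against.** The strongest reply is that covariates enter only in secondary analyses. The model as first described holds arm and time alone, and its one two-way interaction, arm-by-time, is worth testing. On that reading the false-positive risk is about 14% over the three repeated outcomes. This stands as a limit on the concern. It does not remove it, because the sentence on testing all two-way interactions directly follows the covariate sentence and is not confined to arm and time. With only those two factors, each repeated-outcome model would have a single interaction and the two single-value models none.

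A second reply is that many of the 42 terms are covariate-by-covariate or covariate-by-time and say nothing about epinephrine. This is fair. For terms involving arm the figure is 42–60%, which is still high. A third is that disclosing low power warns readers. It does, but it does not control false positives.

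A reader might infer more than the documents support:
- **That a false interaction is near certain.** The number of tests is not fixed by the plan, and correlation between outcomes lowers the probability.
- **That the arm effect will lose half its power.** The plan speaks of investigating interactions, not retaining them, and specifies neither reference coding nor reading the arm effect from such a model.
- **That every interaction is tested again by Cox regression.** That sentence is permissive and mentions neither two-way terms nor significance.
- **That no interaction could be detected.** The 32% applies to a 5% interaction; larger ones are not addressed.

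**Conclusion.** The concern holds in this form: a stated rule to test all two-way interactions, without multiplicity control and with conceded low power, makes at least one chance finding likely. Its size is 73–88% over about 42 tests, and 42–60% for the 18 terms involving arm. These figures assume exactly three covariates, one degree of freedom per term and α=0.05 for each test. If only arm-by-time is tested, the figure is about 14%.

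The effect on power for the arm comparison is a possibility that the wording leaves open, not a consequence of the plan. It falls from 81% to 52% by formula with one reference-coded balanced binary covariate. In simulation it falls from about 78% to 35–38% with two or more interactions kept. With centred coding the loss is negligible. The trial's validity is not in question, but the sentence should be changed before analysis.

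**What to change.** Replace the sentence on interactions in the Statistical analysis plan with:

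> In the three repeated-outcome models (PEFR/CAS, respiratory rate, heart rate) the only interaction tested is arm-by-visit; the primary effect is the arm contrast at t15. For hours of albuterol and ED length of stay, and in Cox models, the arm effect is taken from models without interactions. Arm-by-age and arm-by-gender estimates are reported with 95% CIs as exploratory, without significance claims; covariate-by-covariate and covariate-by-time interactions are not tested.

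Naming the t15 contrast matters because arm-by-visit stays in the model: with visit reference-coded, the raw arm coefficient would be the effect at one visit that nobody had specified. The contrast also matches the time point of the primary outcome. The sentence on Cox regression should be brought into line.

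The cost is wording and somewhat less analysis. What is given up is a set of exploratory interaction tests that the plan itself says are underpowered. About 14% false-positive risk remains over the three arm-by-visit tests if they are independent, so these too should be read with caution.

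### Two secondary outcomes worded as yes/no are assigned both negative binomial and logistic regression, with no count defined, no rule on which result counts and no stated handling of three readings per child

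*Combined protocol and SAP*

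**What the plan says.** The sentence at issue is in the Statistical analysis plan: "Negative binomial regression and logistic regression techniques will also be used to evaluate (7) need for supplemental oxygen and (8) need for albuterol". The numbers refer to the list under Secondary outcome measures.

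- Item 7 begins "Need for supplemental oxygen at" the 60-, 90- and 120-minute readings, and the need is "defined as a room air pulse oximetry of <93"%. That is a threshold, so each reading is yes or no.
- Item 8 is worded as a need for albuterol at the same three times. No number of doses or amount is attached to it.
- Item 9, "Number of hours of albuterol therapy", is a separate outcome with its own mixed linear model.

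The same section sends categorical variables to Fisher's exact and rank tests. It treats time as a repeated-measures effect for the five mixed linear models, but says nothing similar for items 7 and 8. The Power calculation section says that logistic regression will assess "the association between group assignment and dichotomized outcomes". It does not name items 7 and 8, and it ranks no model over another.

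**The concern.** Negative binomial regression is a count model whose variance is at least the mean. A 0/1 variable with event probability p has mean p and variance p(1−p), which is always smaller. The model therefore credits the data with more noise than they have. Its model-based confidence intervals are too wide, and its tests reject too rarely.

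The pairing adds a second problem. The two models estimate different quantities (a rate ratio and an odds ratio) and can disagree on significance. With no ranking, the result to report could be chosen after both are seen. Third, each child gives three correlated readings, and the plan does not say whether they are analysed separately, combined or clustered.

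**Working it through.** **Inputs.** The Power calculation section gives 60 recruited and 54 analysed, allocated equally. With equal loss that is n = 54/2 = 27 per arm. No event rate appears anywhere, so every rate below is assumed. Within-child correlation is also assumed.

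**The plan's own figure.** No precision or power is given for the negative binomial analysis. The nearest figure is 80% power for an odds ratio of 1.58 with n = 54 by logistic regression. It does not reproduce: a two-sided comparison of two proportions at 27 per arm has 6–13% power over control rates of 5–90%. That is a separate problem, and nothing below relies on it.

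**Step 1: standard errors.** On 0/1 data the maximum-likelihood dispersion goes to zero, so the model becomes Poisson. With a and c events in the two arms, the standard error of the log risk ratio is:

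- Poisson limit: √(1/a + 1/c)
- correct (binomial): √(1/a + 1/c − 2/n)

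With equal rates the ratio is √(2/(np)) ÷ √(2(1−p)/(np)) = 1/√(1−p).

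| Assumed need p | SE ratio | Excess |
|---|---|---|
| 5% | 1.03 | 3% |
| 10% | 1.05 | 5% |
| 20% | 1.12 | 12% |
| 50% | 1.41 | 41% |
| 70% | 1.83 | 83% |
| 80% | 2.24 | 124% |

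With unequal rates:

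- 25% vs 50% (a = 6.75, c = 13.5): √0.2222 = 0.471 against √(0.2222 − 0.0741) = 0.385, a ratio of 1.22.
- 50% vs 80% (a = 13.5, c = 21.6): √0.1204 = 0.347 against √(0.1204 − 0.0741) = 0.215, a ratio of 1.61.

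A fitted example with 16/27 against 10/27 events agrees. The estimated dispersion was about 0.00005 and the negative binomial fit could not return standard errors. The Poisson limit gave 0.403. The correct value is 0.297, and robust errors on the Poisson fit also gave 0.297.

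**Step 2: power and disagreement.** These come from exact enumeration of all outcomes at 27 per arm at a single reading, with two-sided 5% Wald tests for both models.

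| Need in the two arms | Negative binomial (Poisson limit) | Logistic | Disagree on significance |
|---|---|---|---|
| 25% vs 50% | 25% | 45% | 19% |
| 40% vs 70% | 22% | 58% | 36% |
| 50% vs 80% | 15% | 62% | 48% |
| 10% vs 40% | 51% | 68% | 17% |

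**Step 3: type I error, same method.** At 20% need in both arms the Poisson-limit Wald test rejects 1.1% of the time (logistic 3.8%). At 50% it rejects 0.5% (logistic 4.1%), and at 70–80% less than 0.1%.

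**Step 4: three readings per child.** If the readings were pooled as independent in ordinary logistic regression, the variance would be understated by a factor of 1 + 2ρ. Type I error would then be 2[1 − Φ(1.96/√(1 + 2ρ))]:

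- ρ = 0.3: 1.96/√1.6 = 1.55, giving 12%.
- ρ = 0.7: 1.96/√2.4 = 1.27, giving 21%.

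**The case against.** The best defence is that the sentence is compressed. The Study data section records the amount and timing of bronchodilator treatment, so a count could be derived. The Power calculation section mentions a dichotomised version of some outcomes. Negative binomial regression might be meant for a count and logistic regression for its yes/no form. This is possible, but no count is defined, the sentence attaches both models to the need itself, and albuterol hours are handled elsewhere. A count of readings with need (0 to 3) would not settle it either. Its variance-to-mean ratio is (1−p)(1+2ρ), which is 1.6 at p = 0.2 and ρ = 0.5 but 0.6 at p = 0.7 and ρ = 0.5, so overdispersion cannot be taken for granted. The defence softens the point to missing specification; the text still needs correcting.

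Several qualifications stand in full:

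- A reader might infer that the standard errors are much too wide whatever the data. That needs common outcomes and model-based errors. If oxygen need after treatment is 20% or less, the excess is 12% or less, and robust errors would remove it. The plan specifies neither kind of error.
- Part of the low type I error at low rates comes from the Wald test. At 20% need a Poisson likelihood-ratio test rejects 4.4% of the time, against 1.1% by Wald.
- It does not follow that a real difference would usually be missed. At 20% vs 60% need the Poisson-limit Wald test has 68% power, and at 10% vs 50% it has 76%. Conversely, logistic regression has only 45% at 25% vs 50%.
- The 12–21% false-positive rate is not a consequence of the plan as written. The plan does not say that the readings are pooled, and they could be analysed one time at a time.

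**Conclusion.** The point holds in this form. A count model is assigned to two outcomes worded as yes/no, beside logistic regression, with no count, no ranking and no stated handling of repeated readings. The direction of the error is certain for model-based standard errors: they are too wide. Its size depends on event rates that the documents do not give. It is minor if need is uncommon. At 50% need or more it is serious, with at least 41% excess in the standard error at equal rates and a fall in power from 62% to 15% at 50% vs 80%. These figures assume 27 analysed per arm and one reading per test; the power comparison also assumes Wald tests for both models. The pooling figure is conditional on a choice that the plan leaves open.

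These are items 7 and 8 of ten listed secondary outcomes. The primary outcome, at 15 minutes, is not affected. The correction should be made because it is specific and cheap and closes a choice that could otherwise be made after seeing results.

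**What to change.** In the Statistical analysis plan:

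1. Delete negative binomial regression for items 7 and 8, or keep it only for a count that is explicitly defined.
2. Name one binary model as the analysis that counts, with the child as the cluster over 60, 90 and 120 minutes. Logistic regression and a log-link model with robust errors are both acceptable. Report the arm effect with its confidence interval.
3. State that any Fisher's exact test on these outcomes is supportive. Otherwise, removing one model still leaves two unranked analyses.

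The cost is a few sentences and no new data. There is a small technical price. With 54 children, robust errors can be too small, so a small-sample correction should be specified. An exact or penalised fallback is also needed in case every child or no child in an arm has the event.
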